2.2.1 Randomization and drug dispensing irregularities

Randomization and drug-dispensing irregularities occur whenever:

1. A randomization is not in accordance with the protocol-defined randomization method, such as a) an ineligible patient is randomized, b) a patient is randomized based on an incorrect stratum, c) a patient is randomized twice, or d) in a dynamic randomization scheme the treatment assignment is, in fact, not random, due to a computer program error.

OR

2. A patient is dispensed an IMP kit not allocated by the protocol-defined randomization, such as a) a patient at any time in the study is dispensed a different treatment kit than as randomized (which may or may not contain the correct-as-randomized IMP), or b) a nonrandomized patient is treated with IMP reserved for randomized patients.

Randomization and drug-dispensing irregularities will be monitored throughout the study and reviewed on an ongoing basis.

All randomization and drug-dispensing irregularities will be documented in the clinical study report. If the number of irregularities is large enough to make a tabular summary useful, the irregularities will be categorized and summarized among randomized patients (number and percentages). Nonrandomized, treated patients will be described separately.

Randomization and drug-dispensing irregularities to be prospectively identified include but are not limited to:

- Kit dispensation without IRT transaction.
- Erroneous kit dispensation.
- Kit not available.
- Randomization by error.
- Patient randomized twice.
- Forced randomization.
- Stratification error.
- Patient switched to another site.

2.3 ANALYSIS POPULATIONS

Patients treated without or before being randomized will not be considered randomized and will not be included in any efficacy population.

The randomized population includes any patient who has been allocated to a study conduct approach group regardless of whether the study conduct approach group is followed.

For any patient randomized more than once, only the data associated with the first randomization will be used in any analysis population. The safety experience associated with any later randomization will be assessed separately.

The safety experience of patients treated and not randomized will be reported separately, and these patients will not be in the safety population.

2.3.1 Efficacy populations

The primary efficacy analysis population will be the intent-to-treat (ITT) population, as defined in the protocol.

2.3.1.1 Intent-to-treat population

The intent-to-treat population is all randomized patients, irrespective of the trial approach group actually being used, analyzed according to the approach group allocated by randomization.

The ITT population will be used to analyze all non-safety endpoints.

2.3.2 Safety population

The safety population is defined as all randomized patients who did actually receive at least one dose of IMP, regardless of the amount of IMP administered.

In the event of patients having followed a trial approach that differed from the one assigned according to the randomization schedule, the safety analyses will be conducted according to the trial approach group assigned by randomization.

Patients will not be considered exposed if there is documented evidence that patients have not taken the study drug:

- If a patient is dispensed IMP and is lost to follow-up without any documented evidence, the patient will be considered exposed and included in the safety population.
- Randomized patients for whom it is unclear whether they took the study medication will be included in the safety population as randomized.

In addition:

- Nonrandomized but treated patients (or treated before being randomization (if any)) will not be part of the safety population; however, their safety data will be presented separately.
- For patients following more than one study approach (virtual and traditional), the patient will be analyzed in the study conduct approach group as randomized.

2.3.3 PRO and ClinRO populations

The analysis of PROs and ClinROs will be conducted on the ITT population.

2.4 STATISTICAL METHODS

Continuous data will be summarized using the number of available data, mean, standard deviation (SD), median, minimum and maximum for each study conduct approach group. For insulin dose and PROs and ClinROs, summary statistics will include quartiles Q1, Q3 and medians.

Categorical and ordinal data will be summarized using the number and percentage of patients in each study conduct approach group.

In general, descriptive statistics of quantitative efficacy and safety parameters (result and change from baseline) by scheduled post-baseline visits will be provided on observed cases, ie, the inclusion of only patients having non-missing assessments at a specific visit. All statistical analyses (descriptive statistics, plots, and statistical models) will be performed on visits defined using the time windows provided in [Section 2.5.4](#).

2.4.1 Demographics and baseline characteristics

Parameters described in [Section 2.1.1](#) will be summarized by study conduct approach group and overall using descriptive statistics.

Parameters will be summarized on the randomized population analyzed in the study conduct approach group to which patients were randomized.

Medical/surgical history will be classified into primary system organ class (SOCs) and HLTs using MedDRA and will be summarized by study conduct approach groups. Events will be sorted by SOC internationally agreed order and decreasing frequency of HLT based on incidence in the overall population.

P-values on demographic and baseline characteristic data will not be calculated.

2.4.2 Prior or concomitant medications

The prior, concomitant and post-treatment medications will be presented on the randomized population, separately for anti-diabetic medications and non-anti-diabetic medications. Anti-diabetic medications will be identified by a pre-defined list of ATC codes.

Medications will be summarized by treatment group and overall (only for prior medications) according to the WHO-DD dictionary. Non-anti-diabetic medications will be summarized considering the first digit of the ATC class (anatomic category) and the first 3 digits of the ATC class (therapeutic category). All ATC codes corresponding to a medication will be summarized, and patients will be counted once in each ATC category (anatomic or therapeutic) linked to the medication. Therefore patients may be counted several times for the same medication. Anti-diabetic medications will be presented by pharmacological class (ATC3), chemical class (ATC4), and standardized medication name.

The tables for prior medications will be sorted by decreasing frequency within the ATC categories presented based on the overall incidence across treatment groups. In case of equal frequency, alphabetical order will be used.

The tables for concomitant and post-treatment medications will be sorted by decreasing frequency within the ATC categories presented based on the incidence in the Virtual group. In case of equal frequency, alphabetical order will be used.

Frequency statistics including number of patients and percentage will be provided. No statistical test for the between-group difference will be performed.

2.4.3 Extent of investigational medicinal product exposure and compliance

The extent of IMP exposure and compliance will be assessed and summarized by study conduct approach actual group within the safety population ([Section 2.3.2](#)).

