11.2 DISPOSITION OF PATIENTS

Screened patients are defined as any patient who met the inclusion criteria and signed the informed consent.

Randomized patients consist of all screened patients with a trial approach group allocated and recorded in the IRT database, regardless of whether the treatment kit was used or not.

For any patient randomized more than once, only the data associated with the first randomization will be used in any analysis population. The safety experience associated with any later randomization will be assessed separately.

The safety experience of patients treated and not randomized will be reported separately, and these patients will not be in the safety population.

The total number of patients for each of the following categories will be presented.

- Screened patients
- Screen failure patients and reason for screen failure
- Randomized patients
- Safety population ([Section 11.3.2](#)) presented as treated
- The intent-to-treat (ITT) population ([Section 11.3.1](#)) analyzed as randomized
- The randomization strata (sites and screening HbA1c categories [$<7.6\%$, $\geq 7.6\%$] assigned by IRT); the discrepancy between the strata assigned by IRT and the information reported on e-CRF will be listed for all randomized patients

- Patients who permanently discontinued the IMP, and the reasons for permanent treatment discontinuation
- Patients who completed the 24-week treatment period (patients who have attended Visit 12, who did not permanently discontinue treatment, and who did not take any rescue medication)
- Patients who did not complete the 24-week treatment period
- Patients who discontinued 24-week treatment by main reason for permanent treatment discontinuation
- Patients who completed the study (patients who have attended Visit 12, whichever the treatment duration)
- Patients who did not complete the study (patients who have not attended Visit 12)
- Patients who discontinued the study by main reason for study discontinuation

For all categories of patients except screened and screen failure patients, percentages will be calculated using the number of randomized patients as denominator for each approach group.

Patients with the following deviations will be identified and described in separate listings:

- Treated but not randomized
- Randomized but not treated
- Randomized but not treated as randomized

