11.3.2 Safety population

The safety population is defined as all randomized patients who did actually receive at least one dose of IMP, regardless of the amount of IMP administered.

In the event of patients having followed a trial approach that differed from the one assigned according to the randomization schedule, the safety analyses will be conducted according to the trial approach group assigned by randomization.

Patients will not be considered exposed if there is documented evidence that patients have not taken the study drug:

- If a patient is dispensed IMP and is lost to follow-up without any documented evidence, the patient will be considered exposed and included in the safety population
- Randomized patients for whom it is unclear whether they took the study medication will be included in the safety population as randomized

In addition:

- Non randomized but treated patients will not be part of the safety population, but their safety data will be presented separately

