11.4.1 Extent of study treatment exposure and compliance

The extent of study treatment exposure and compliance will be assessed and summarized by randomized trial approach group within the safety population.

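### SAP 2.4.3 groups exposure and compliance by an undefined actual approach group, against the as-randomized rule in protocol 11.4.1 and SAP 2.3.2

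*SAP*

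**What the plan says.** **Exposure and compliance.** SAP 2.4.3 says that they "will be assessed and summarized by study conduct approach actual group within the safety population" and refers to SAP 2.3.2 for that population. Protocol 11.4.1 covers the same analysis in almost the same sentence, but there they "will be assessed and summarized by randomized trial approach group within the safety population".

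**Safety population.** Protocol 11.3.2 and SAP 2.3.2 share a rule for patients who followed an approach other than the one assigned: "the safety analyses will be conducted according to the trial approach group assigned by randomization". SAP 2.3.2 adds that, for anyone following both approaches, "the patient will be analyzed in the study conduct approach group as randomized".

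**Status of compliance.** Protocol 9.2.1.5 and SAP 2.1.3.3 name medication compliance, expressed as IMP exposure time and percentage of prescribed dose, as a secondary endpoint. Protocol 11.4.3.1.2 sends its analysis to 11.4.1.1. For endpoints outside safety, SAP 2.3.1.1 says: "The ITT population will be used to analyze all non-safety endpoints". That population is analyzed by allocated group.

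**Switching.** SAP 2.2 plans a separate listing of patients who changed approach after randomization.

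**Declared changes.** SAP 1.5 and 1.6 both read as not applicable.

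**A related label.** In its list of disposition counts, protocol 11.2 describes the safety population as "presented as treated".

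**The concern.** The trial compares two ways of running a study. All patients take the same basal insulin, so an actual group cannot mean the drug received. It can only mean the conduct approach followed, which is what was randomized. Grouping by it gives up the randomized comparison for any patient who switched.

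Two outputs are exposed.

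- **Compliance.** Patients who find an approach hard to follow may be likelier both to leave it and to miss doses. The documents do not say so, but if it is true, the literal rule would credit their non-compliance to the other arm.
- **Patient-years.** SAP 2.4.3.1 reports cumulative exposure in patient-years, under the grouping of 2.4.3. SAP 2.4.5.1 reports hypoglycemia events per patient-year in the safety population, which SAP 2.3.2 analyzes as randomized. With a switcher, the two sets of patient-years per arm would differ unless movements in opposite directions happened to cancel.

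The programmer also faces two instructions for the same patient, with no definition of the term that would settle which applies.

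**Working it through.** No figure in the plan bears on this point. The only design figure is the HbA1c precision, and it does not enter. The check is a comparison of texts, followed by arithmetic on assumed inputs to show scale.

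**Step 1: same analysis, two groupings.** Protocol 11.4.1 and SAP 2.4.3 agree on content (exposure and compliance) and on population (safety). They differ on grouping: randomized in the protocol, actual in the SAP. SAP 1.5 and 1.6 record no change.

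**Step 2: the SAP against itself.** SAP 2.4.3 takes its population from 2.3.2. That section gives the SAP's only explicit rule for patients who depart from their approach, and the rule is as randomized.

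**Step 3: what literal reading does to patient-years.** The documents give neither the arm split of the 15 randomized patients nor the number of switchers, so both are assumed here, with equal exposure per patient. One switcher changes the arm left by −1/n and the arm joined by +1/m.

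| Assumed split n/m | After one switch | Arm left | Arm joined |
|---|---|---|---|
| 7/8 | 6/9 | −1/7 = −14.3% | +1/8 = +12.5% |
| 5/10 | 4/11 | −1/5 = −20% | +1/10 = +10% |
| 75/75 (planned) | 74/76 | −1/75 = −1.3% | +1/75 = +1.3% |

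**Step 4: what it does to compliance at the planned size.** Suppose that, as randomized, compliance below 80% occurs in 10/75 virtual (13.3%) and 5/75 traditional (6.7%) patients. Let k virtual patients switch, all of them non-compliers. The actual-group shares are then (10 − k)/(75 − k) and (5 + k)/(75 + k).

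| k | Virtual | Traditional | Direction |
|---|---|---|---|
| 0 | 10/75 = 13.3% | 5/75 = 6.7% | as randomized |
| 1 | 9/74 = 12.2% | 6/76 = 7.9% | same |
| 2 | 8/73 = 11.0% | 7/77 = 9.1% | same |
| 3 | 7/72 = 9.7% | 8/78 = 10.3% | reversed |
| 5 | 5/70 = 7.1% | 10/80 = 12.5% | reversed |

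If instead 5 patients switch at the arm's own rate, they carry 5 × 10/75 = 0.67 non-compliers. The shares become 9.33/70 = 13.3% and 5.67/80 = 7.1%, so the direction holds.

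**Step 5: the same at 15 patients.** Assume an 8/7 split with non-compliance in 2/8 (25%) virtual and 1/7 (14.3%) traditional patients. One non-compliant virtual patient who switches gives 1/7 (14.3%) and 2/8 (25%). One patient can exchange the two percentages, though with arms this small the percentages carry little weight in either order.

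**The case against.** The strongest reply is that SAP 2.3.2 already settles the matter. A patient who switches has followed more than one approach, 2.3.2 says that such a patient is analyzed as randomized, and 2.4.3 cites that section. On this reading nobody moves, and the flaw is one stray word. That is a fair reading, but it requires the reader to ignore a word in 2.4.3 that departs from the protocol's wording. The text should not depend on that choice.

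The reply is right on four further matters:

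- The documents give no switching rate and describe no procedure for changing approach. After the initial examination, unscheduled on-site visits in the virtual arm are for safety assessment only (protocol section 10 and flow chart footnote e). A planned deviation listing shows that switching was foreseen, not that it was common.
- Compliance was always to be described, never tested. SAP section 2 now records early termination at 15 randomized patients, with basic descriptive tables or listings only.
- The switcher listing exists already, so a reader of the report could see who moved.
- A reader might infer from protocol 11.2 that the safety analyses themselves are run as treated. The documents do not support this. The phrase labels one line in a list of disposition counts, protocol 11.3.2 makes the safety analyses as randomized, and the SAP's own disposition section omits the label. It is a minor inconsistency within the protocol.

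**Conclusion.** The contradiction stands, both between SAP and protocol and within the SAP. It concerns a named secondary endpoint and was not declared as a change.

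Its numerical effect cannot be stated, because the number of switchers is not given. It is zero if nobody switched. With an assumed 7/8 split of the 15 patients and equal exposure, one switcher would shift patient-years by about 14% in one arm and 12.5% in the other. The primary HbA1c analysis is by allocated group and is not touched.

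A reader might go further and infer that the compliance comparison would be biased or reversed. The documents do not support that. The reversals under working rest wholly on assumed inputs: with 75 per arm and the shares chosen there, at least three switchers are needed, all of them non-compliers and all moving the same way. At 15 patients one could suffice, but only under an assumed split and assumed counts. Reversal is a hypothetical consequence of the literal wording, not a finding about this trial.

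**What to change.** In SAP 2.4.3, replace the reference to the actual group with the approach group as randomized, so that it agrees with protocol 11.4.1 and SAP 2.3.2. Keep the listing of switchers in SAP 2.2 as it is.

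If grouping by approach followed was intended, define it (including where a patient who followed both approaches is counted), present it as supplementary to the as-randomized table, and declare it in SAP 1.6.

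The label in protocol 11.2 can be aligned with 11.3.2 if the protocol is revised for another reason. It does not justify an amendment of its own, since protocol section 15 requires a written, signed amendment with ethics review.

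The cost is one phrase in the SAP, with no new data and no new analysis.

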2.4.3.1 Extent of investigational medicinal product exposure

The extent of IMP exposure will be assessed by the duration of IMP exposure.

The duration of exposure to the IMP during the study will be the total number of days of administration of IMP, ignoring temporary drug discontinuation (see [Section 2.5.3](#) for calculation in case of missing or incomplete data) and is defined as:

(Date of the last IMP administration – date of the first IMP administration) + 1

Duration of IMP exposure will be summarized descriptively as a quantitative variable (number, mean, SD, median, minimum, and maximum). In addition, duration of treatment exposure will also be summarized categorically by numbers and percentages for each of the following categories and cumulatively according to these categories:

- up to 4 weeks.
- >4 to 8 weeks.
- >8 to 12 weeks.
- >12 to 16 weeks.
- >16 to 20 weeks.
- >20 to 22 weeks.
- >22 to 23 weeks.
- >23 to 24 weeks.
- >24 weeks.

Additionally, the cumulative duration of treatment exposure will be provided, defined as the sum of the duration of treatment exposure for all patients, and will be expressed in patient years.

2.4.3.2 Daily insulin doses

The process described in [Section 2.5.4](#) will be applied to assign visits to the insulin doses transferred from the e-diary into the clinical database, and to retrieve doses in case of premature treatment discontinuation.

At each visit, the average daily basal, mealtime, and total (basal plus mealtime) insulin doses (U and U/kg body weight) will be calculated as the mean of daily insulin doses collected in the week before the visit. No minimum number of available doses will be required. Technical details related to the computation and handling of missing data are described in [Section 2.5.3](#).

The daily insulin doses (basal, mealtime, total) will be described at each visit, as well as the changes from baseline, relative change from baseline and change from previous visit.

The calculation of daily insulin doses at baseline is defined in [Section 2.1.1](#).

2.4.3.3 Compliance

A given administration will be considered noncompliant if the patient did not take the planned dose of treatment as required by the protocol. No imputation will be made for patients with missing or incomplete data.

Percentage of compliance for a patient will be defined as the exposure duration of study minus number of days with a dose equal to 0 divided by the duration of the IMP exposure.

Treatment compliance will be summarized descriptively as quantitative variables (number, mean, SD, median, minimum, and maximum). The percentage of patients whose compliance is <80% will be summarized.

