
ENDPOINT(S)
	
Primary endpoint:
 
Changes in HbA1c from baseline to Week 24
 
Secondary endpoints:
 
Study methodology assessment with the two approaches:
 
 • Patient satisfaction with trial experience PRO: Was it Worth It (WIWI) Questionnaire at Week 24 • The effect of the trial on a patients' ability to work and perform regular activities PRO: Work Productivity and Impairment-study participation (WPAI-SP), change from baseline to Week 24 • Patient burden with the trial participation: (PRO: Overall Study Experience-Participation [OSEP]), change from baseline to Week 24 (OSEP part 1-diabetes appraisal)/at Week 24 (OSEP part 2-study appraisal) • Patient-reported healthcare resource utilization: resource use questionnaire (RUQ) over the 24 week treatment period • Medication and key study activity compliance from baseline to Week 24: 
 - The exposure time to basal insulin (Toujeo) and percentage of actual dose over the prescribed dose - The number of times the patient used the Bluetooth devices, in accordance with the study instructions - The number of times the patient completed the blood draw visit, in accordance with the study instructions - Patient withdrawal from baseline to Week 24 
Diabetes control with the two approaches:
 
 • Diabetes related PROs, changes from baseline to Week 24 in: 
 - Diabetes Treatment Satisfaction Questionnaire status (DTSQs)

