	
patients, irrespective of the trial approach group being used, analyzed according to the approach group allocated by randomization.
 
The safety population is defined as all randomized patients who did actually receive at least one dose of Toujeo, regardless of the amount of Toujeo administered.
 
Primary analysis:
 
The primary efficacy endpoint (change in HbA1c from baseline to Week 24) will be analyzed using a mixed-effect model with repeated measures (MMRM) approach, using the missing at random framework carried out via SAS PROC MIXED using adequate contrasts. The model will include fixed categorical effects of trial approach group, visit, trial approach-by-visit interaction, randomization stratum of site; and the continuous fixed covariates of baseline HbA1c value and baseline HbA1c value-by-visit interaction.
 
Analysis of secondary endpoints:
 
A descriptive summary will be provided for each endpoint per approach group. Additional statistical analyses are summarized below.
 
Analysis of study methodology
 
The change in WPAI-SP and OSEP part 1 scores from baseline to Week 24 will be analyzed using an analysis of covariance (ANCOVA). WIWI and OSEP part 2 scores will be compared at Week 24 between approach groups using an analysis of variance (ANOVA).
 
The total and average resource utilization per patient will be calculated on all on-treatment questionnaires using the RUQ.
 
Duration of IMP exposure will be summarized descriptively and categorically (by periods) by numbers and percentages.
 
The number of times the patient used the Bluetooth devices and the number of times the patient completed the blood draw visit will be summarized only in the virtual approach group.
 
Patient withdrawal from baseline to Week 24 will be analyzed descriptively and using a Kaplan-Meier plots/estimates of the cumulative incidence of study discontinuation.
 
Analysis of diabetes control
 
The change in DTSQs, HFS-II, and DDS scores from baseline to Week 24 will be analyzed using an ANCOVA. DTSQc scores at Week 24 will be compared between approach groups using an ANCOVA.
 
The change in HbA1c from baseline to Week 16 will be described in each trial approach group and analyzed using the same model as done for primary endpoint
 
The change in FPG, and 7-point SMPG from baseline to Week 24 will be described in each trial approach group and analyzed using an MMRM approach.
 
Analysis of patient care

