11.4.1.2 Compliance

A given administration will be considered noncompliant if the patient did not take the planned dose of treatment as required by the protocol. No imputation will be made for patients with missing or incomplete data.

Treatment compliance percentage will be summarized descriptively (N, Mean, SD, Median, Min, and Max). The percentage of patients with compliance is <80% will be summarized.

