11.4.3.1.2 Analysis of compliance with IMP

See [Section 11.4.1.1](#).

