2.1.3.3 Secondary endpoints related to compliance

The following additional endpoints will be considered:

- Compliance with medication during the treatment period (from Day 1 to Week 24), expressed in terms of IMP exposure time and the percentage of actual dose over the prescribed dose
- Compliance with key study activities during the treatment period (from Day 1 to Week 24), including:
 - Number of times the patient used the Bluetooth devices in accordance with the study instructions
 - Number of times the patient completed the blood draw visits (Visit 10 and Visit 12) in accordance with the study instructions
 - Patient withdrawal during the treatment period (from Day 1 to Week 24)

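### The SAP's compliance percentage counts every non-zero dose as compliant, so it does not measure the secondary endpoint of actual over prescribed dose, and neither document derives that ratio

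*SAP*

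**What the plan says.** **The endpoint.** The protocol synopsis lists, under medication compliance, "The exposure time to basal insulin (Toujeo) and percentage of actual dose over the prescribed dose". Protocol 9.2.1.5 repeats this, and SAP 2.1.3.3 keeps it as a secondary endpoint, "expressed in terms of IMP exposure time and the percentage of actual dose over the prescribed dose".

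**The derivation.** SAP 2.4.3.3 opens with a rule for a single administration: "A given administration will be considered noncompliant if the patient did not take the planned dose of treatment as required by the protocol". It continues: "No imputation will be made for patients with missing or incomplete data". It then gives the only compliance formula in either document: "the exposure duration of study minus number of days with a dose equal to 0 divided by the duration of the IMP exposure". The result is summarized as a continuous variable and as the percentage of patients below 80%.

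**The protocol's analysis text.** Protocol 11.4.1.2 has the same administration-level rule and announces a compliance percentage, but gives no formula. Protocol 11.4.3.1.2, headed "Analysis of compliance with IMP", refers only to the exposure section, 11.4.1.1. For IMP, the synopsis's analysis paragraph plans exposure duration alone: "Duration of IMP exposure will be summarized descriptively and categorically (by periods) by numbers and percentages".

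**Grouping.** SAP 2.4.3 summarizes exposure and compliance by actual approach group. Protocol 11.4.1 specifies the randomized group for the same summary, and SAP 2.3.2 analyses safety as randomized. SAP 1.5 and 1.6 record no modifications.

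**The concern.** The formula uses the actual dose only to decide whether it was zero. Any injected amount, well below or well above what was prescribed, makes the day fully compliant. That departs from the named endpoint and also from the opening sentence of the same SAP section, under which an administration that misses the planned dose is noncompliant.

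Medication compliance is one of the secondary objectives on which virtual and traditional conduct are to be compared, and Protocol section 4 lists IMP adherence among the things the pilot should inform. A percentage that stays at 100% unless zeros are recorded would be read as evidence of good dosing compliance in both groups, while the dose-ratio half of the endpoint would go unreported without any statement to that effect.

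The grouping mismatch is a smaller, separate matter. A patient who changed approach would be counted in one group for compliance and in the other for the remaining safety-population summaries.

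**Working it through.** The documents state no compliance figure to reproduce, so the check applies the SAP formula to simple dosing patterns and then looks for the ratio elsewhere.

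**Inputs**
- E = exposure days = last minus first IMP date, plus 1 (SAP 2.4.3.1). Assumed 24 × 7 = 168.
- Z = days with dose 0 (SAP 2.4.3.3).
- Flag: below 80% (SAP 2.4.3.3).
- Illustrative assumption: a constant prescribed dose.

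**Formulas**
- SAP score = 100 × (E − Z)/E. The SAP text has no brackets. Without them, Z = 17 would give 168 − 17/168 = 167.9, which is not a percentage, so the bracketed reading is used.
- Named endpoint = 100 × sum of actual dose / sum of prescribed dose.

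| Pattern over 168 days | SAP score | Actual/prescribed |
|---|---|---|
| 90% of prescribed every day | 168/168 = 100% | 90% |
| 50% every day | 100% | 50% |
| 150% every day | 100% | 150% |
| 17 zero days, 75% on the rest | 151/168 = 89.9% | 151 × 0.75/168 = 67.4% |
| 17 zero days, full dose on the rest | 89.9% | 89.9% |

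In these patterns the two measures agree only when every non-zero dose equals the prescribed dose.

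**When the flag is reached.** With E = 168, Z = 33 gives 135/168 = 80.4% and Z = 34 gives 134/168 = 79.8%, so 34 zero-dose days are needed. Week 24 is targeted at Day 169 (SAP 2.5.4) with a visit window of ±3 days, so E could run from 166 to 172. The threshold is 34 days for E = 166 to 169 and 35 for E = 170 to 172 (at E = 170, Z = 34 gives exactly 80.0%). Under-dosing without recorded zeros never triggers the flag.

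**Is the ratio derived elsewhere?**
- Protocol 11.4.1.1 and SAP 2.4.3.1 derive exposure time. That half of the endpoint is complete.
- SAP 2.4.3.2 and 2.5.3 give average actual doses in U and U/kg, with no prescribed dose.
- SAP 2.1.1 puts planned and actual basal dose together, but only at baseline.
- The general conventions in SAP 2.5.1 add nothing.

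The dose half therefore has no derivation.

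**Days without a record.** SAP 2.4.3.3 does not name the source of zero-dose days or say how a day without a record counts. Protocol 9.2.2.3 requires daily diary dosing to Week 12 and then at least the week before each visit. With visits at Weeks 16, 20 and 24, the diary minimum is 84 + 21 = 105 of 168 days. This is a minimum for one source, not a count of missing days.

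**The case against.** The strongest defence is practical. Toujeo is titrated at the investigator's discretion, patients are asked to self-titrate (Protocol 10.1.2.2), and well-trained patients may be allowed to adjust between visits without consulting the site (Protocol 8.1.6). A dose below the last recommendation may therefore be within protocol, and a prescribed dose may not exist for many days. Counting days without a dose is then a reasonable simple measure, and SAP 2.4.3.2 still reports actual doses. This stands as a reason why the ratio may not be evaluable. It does not justify presenting another quantity as the endpoint's compliance percentage.

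SAP section 2 also says that, after early termination, only basic descriptive output will be produced. That limits the consequence, but it neither replaces the formula nor supplies the ratio.

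Three stronger readings are tempting and are not supported:
- **A reader might infer that the 63 days outside the diary minimum (168 − 105) are scored as compliant.** The no-imputation sentence could instead mean that no percentage is derived for patients with incomplete data. Doses are also asked about at every contact, checked against returned pens and entered in the e-CRF (Protocol 8.7.1 and 10.1.3). The size of any effect is unknown.
- **A reader might infer that temporary stops are captured only when the investigator decides on them and more than one dose is missed.** Protocol 10.3.1 requires any temporary discontinuation to be entered in the diary and the duration of all of them in the e-CRF. The more-than-one-dose sentence only defines an investigator-decided stop.
- **A reader might take the as-treated label in Protocol 11.2 as a second grouping rule for this analysis.** It is a disposition line that SAP 2.2 does not carry forward. The conflict that matters is the word for actual group in SAP 2.4.3.

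**Conclusion.** The SAP's compliance percentage is wrong as written for the endpoint it serves. It omits the prescribed dose, contradicts the planned-dose rule in its own section, and leaves the actual-over-prescribed ratio without a derivation in either document. Under the assumption of 168 exposure days and a constant prescribed dose, the discrepancy can be as large as 100% reported against 50% actual, or any other ratio, provided no zero is recorded.

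The treatment of days without a record is an ambiguity to be settled, not an established error. The grouping conflict is real but matters only if a patient changes approach, and SAP 2.2 lists such patients separately.

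Severity is low to moderate: one secondary, descriptive output in 15 randomized patients, with no effect on the primary endpoint.

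**What to change.** 1. Relabel the SAP 2.4.3.3 measure as *percentage of exposure days without a recorded zero dose*, and do not report it as the dose-ratio endpoint.
2. Where both prescribed and actual Toujeo doses are documented, report 100 × sum of actual / sum of prescribed units, and also the percentage of days at the planned dose, with the number of evaluable days per patient. The second measure is needed because errors cancel in the sum: 84 days at 50% and 84 days at 150% give (42 + 126)/168 = 100%, yet no day is at the planned dose. Where the doses are not documented, state that the dose-ratio part is not evaluable.
3. Take zero-dose days from the diary together with the e-CRF dosing and temporary-discontinuation records, count days with no record as unknown, and state which measure the below-80% table uses.
4. Correct SAP 2.4.3 so that exposure and compliance are summarized by randomized approach group, in line with Protocol 11.4.1 and SAP 2.3.2.

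The cost is minor SAP wording and programming for 15 patients. The main effort is in item 2. A planned dose in the e-CRF is explicit only at baseline (SAP 2.1.1), so later prescribed doses may have to be taken from the titration recommendations in source files (Protocol 10.2.1). With self-titration, not evaluable may be the usual result, which is why the relabelling comes first.
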